5.3. Prior and Concomitant Medications

All prior medications, dictionary coded by WHO-DD, will be descriptively summarized by patient group for the study. Summaries will present patient counts (and percentages) for all prior medications, by decreasing frequency of the overall incidence of ATC followed by therapeutic class. In case of equal frequency across anatomical or therapeutic categories, alphabetical order will be used. Patients will be counted once in each ATC category (anatomical or therapeutic) linked to the medication, but may be counted several times for the same medication. Prior LMT (statins and non-statin) and CV medication use will also be summarized.

All concomitant medications during the study, dictionary coded by WHO-DD, will be descriptively summarized by patient group for the study. Summaries will present patient counts (and percentages) for the concomitant medication groups described in Section 4.3 for all concomitant medications (including statin, LMT, CV), by decreasing frequency of the evinacumab group incidence of ATC followed by therapeutic class. In case of equal frequency across anatomical or therapeutic categories, alphabetical order will be used. Patients will be counted once in each ATC category (anatomic or therapeutic) linked to the medication, hence may be counted several times for the same medication. Additionally, concomitant medications pre-specified from e-CRF as statin, LMT, and CV will be summarized by patient counts (and percentages) for the standardized medication names.

Post-treatment medications will be summarized as described above for all medications.

The summary of prior and concomitant medications will be provided for all patients in the study in the safety analysis set, and again for the subpopulation of adolescent patients.

5.4. Prohibited Medications

Listing of prohibited medications will be provided for the patients in the safety analysis set for the study.

5.5. Patient Disposition

Patient disposition includes the description of patient status at major milestone decisions in the study, as well as the patient analysis populations.

Patient study status for the study will be summarized by patient group for the study (screened patients, screen failures, and non-enrolled but treated patients only). Summaries will provide the frequency (and percentage as applicable) of patients that met the criteria for the variables described in Section 4.5. Exception listings will be generated for any patient treated but not enrolled, enrolled but not treated.

All patient analysis populations will be summarized by patient group for the study, depicting frequencies (and percentages) of patients that met the criteria for each population described in Section 3.

The incidence of premature study treatment discontinuation (irrespective of the reason) and premature treatment discontinuation due to AEs will be presented graphically by patient group for the study in the safety analysis set using the Kaplan-Meier method.

The summary of patient disposition will be provided for all patients in the study in the safety analysis set, and again for the subpopulation of adolescent patients.

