1.2. Study Objectives

1.2.1. Primary Objectives

The primary objectives of the study are:

- To evaluate the long-term safety and tolerability of evinacumab 15 mg/kg IV administered Q4W in patients with HoFH.
- To evaluate the long-term safety and tolerability of evinacumab 15 mg/kg IV administered Q4W in adolescent patients with HoFH

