4.5. Patient Disposition

Patient disposition will include the description of patient status at major milestone decisions in the study, as well as the patient analysis populations.

For patient study status, patient milestone categories are defined below. As applicable, percentages will be calculated using a denominator of the number of patients treated with open-label study treatment, with two exceptions. Specifically, the two exceptions will be for the screened and screen failure categories, which will not have associated percentages shown.

- The total number of screened patients: defined as originally having met the inclusion criteria and signed the ICF
- The total number of patients failed screening
- The total number of patients enrolled, defined as all screened patients with a treatment kit number allocated and recorded in the IVRS database, regardless of whether the treatment kit was used.

- The total number of patients enrolled but not receiving study treatment.
- The total number of patients enrolled and receiving study treatment.
- The total numbers of patients who have participated in a previous evinacumab study (i.e., R1500-CL-1331 and R1500-CL-1629), or evinacumab-naïve patients with HoFH.
- The total number of patients who completed the OLTP as collected on the End of Treatment - Evinacumab e-CRF.
- The total number of patients who prematurely discontinued study treatment during the OLTP, and the reasons for discontinuation collected on the End of Treatment - Evinacumab e-CRF.
- The total number of patients ongoing in OLTP (applicable for the interim analyses)
- The total number of patients who complete the last study follow-up visit (i.e. Follow-up week 24).

The following patient populations for analyses are listed below:

- Safety (SAF) Analysis Set
- Efficacy Analysis Set (same as SAF)
- Pharmacokinetic (PK) Analysis Set
- Immunogenicity (ADA and NAb) Analysis Sets

The following patient listings will provide the details from the patient disposition table.

- A listing of patients treated but not enrolled, patients enrolled but not treated.
- A listing of patients prematurely discontinued from treatment, along with reasons for discontinuation.

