4.7. Primary and Secondary Endpoints

4.7.1. Primary Endpoint

The primary endpoint is the incidence and severity of treatment-emergent adverse events (TEAEs) and other safety variables during the open-label treatment period in patients treated with evinacumab 15 mg/kg IV Q4W.

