4.8. Other Safety Variables

The other safety variables include clinical laboratory data, vital signs, and ECG. Unless otherwise noted, the baseline value is defined according to the definition of baseline specified in Section 6.1.

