- All TEAEs by maximum severity (i.e., mild, moderate or severe)
- A common TEAE related to any clinically significant signal will be further characterized as appropriate. The characterization of the clinically significant signal can include Kaplan-Meier curves for time from first dose to first occurrence of selected TEAE, time to resolution, and event duration. Patients without any event will be censored at the end of the respective TEAE period.

Analysis of all treatment emergent serious adverse event(s)

- All Serious TEAEs by primary SOC, HLG, HLT, and PT
- All Serious TEAEs by primary SOC and PT
- Patient listings of serious TEAEs will be provided in the report appendix.
- All Serious TEAEs relationship (related/not related) to evinacumab
- A serious TEAE related to any clinically significant signal will be further characterized as appropriate. The characterization of the clinically significant signal can include Kaplan-Meier curves for time from first dose to first occurrence of selected TEAE, time to resolution, and event duration. Patients without any event will be censored at the end of the respective TEAE period.

Analysis of all treatment-emergent adverse event(s) leading to treatment discontinuation

- All TEAEs leading to permanent treatment discontinuation, by primary SOC, HLG, HLT, and PT
- All TEAEs leading to permanent treatment discontinuation, by primary SOC and PT

- Patient listings of TEAEs leading to permanent treatment discontinuation will be provided in the report appendix.
- A TEAE leading to permanent treatment discontinuation and related to any clinically significant signal will be further characterized as appropriate. The characterization of the clinically significant signal can include Kaplan-Meier curves for time from first dose to first occurrence of selected TEAE, time to resolution, and event duration. Patients without any event will be censored at the end of the respective TEAE period.

Post-treatment adverse events

- All post-treatment AEs by primary SOC and PT
- All post-treatment SAEs by primary SOC and PT

Analysis of Cardiovascular events

- TEAEs suspected of being CV events by primary SOC and PT
- TEAEs suspected of being CV events categorized by adjudicated outcome of positive, negative, or in-process (as applicable)

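### SAP 5.5 plots discontinuation due to AEs by Kaplan-Meier with no censoring rule, so the curve would read at or above the actual cumulative incidence

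*SAP*

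**What the plan says.** SAP 5.5 announces two curves in one sentence. It opens with "The incidence of premature study treatment discontinuation (irrespective of the reason"), which is the all-reason curve, and continues with the cause-specific one: "premature treatment discontinuation due to AEs will be presented graphically by patient group for the study in the safety analysis set using the Kaplan-Meier". The word incidence governs both. Section 5.5 states no censoring rule, and the SAP names no competing-risk method anywhere. Its only written Kaplan-Meier censoring rule, in SAP 5.8.1, is for the time to selected TEAEs.

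Other displays cover the same events without Kaplan-Meier. SAP 4.5 lists "The total number of patients who prematurely discontinued study treatment during the OLTP, and the reasons for discontinuation", taken from the end-of-treatment e-CRF. SAP 5.8.1 gives the number and percentage of patients with a TEAE leading to permanent discontinuation, patient listings, and tables including "All TEAEs leading to permanent treatment discontinuation, by primary SOC and PT".

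On the status of the outcome, the objective in SAP 1.2.1 is "To evaluate the long-term safety and tolerability of evinacumab 15 mg/kg IV administered Q4W in patients with HoFH", with a parallel objective for adolescents. SAP 4.7.1 states: "The primary endpoint is the incidence and severity of treatment-emergent adverse events (TEAEs) and other safety variables". SAP 4.8 adds: "The other safety variables include clinical laboratory data, vital signs, and ECG". AE discontinuation is named in none of these.

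**The concern.** Protocol 7.3.2.1 allows treatment to stop for reasons that need not be adverse events. Withdrawal of consent is the clearest, and the investigator may also stop dosing at any time in the patient's interest. A patient who has stopped for such a reason cannot later stop because of an AE. A standard Kaplan-Meier curve for AE discontinuation censors that patient, which redistributes the patient's weight to those still on treatment. The curve then describes what would happen if nobody could stop for another reason, and only if those stops are independent of AE risk. That is not the share of treated patients who stop because of an AE, which is what incidence means to a reader of the report.

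What is at stake is the accuracy of one figure. Treatment lasts from months to about 4 years (SAP 2.3), so a crude percentage does not show incidence by a given time. The Kaplan-Meier curve is the planned time-based display of AE discontinuation, and any excess accumulates towards its later part.

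**Working it through.** **Inputs.** The plan has no figure to reproduce: no sample-size calculation was performed (SAP 2.2), and no AE-discontinuation or dropout rate is given. The study plans about 120 patients, about 14 of them adolescents (SAP 2.2). The yearly rates below are assumptions. Censoring of other-reason stops is also an assumption, taken from standard practice.

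**Direction.** At each AE-stop time, let d be the number of AE stops and n the number still on treatment.

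- One minus Kaplan-Meier is the sum of S_AE × d/n, where S_AE, taken just before that time, falls only at AE stops.
- The Aalen-Johansen estimate is the sum of S_all × d/n, where S_all falls at every stop.
- S_all is never above S_AE, so one minus Kaplan-Meier is never below Aalen-Johansen. The two are equal when no other-reason stop precedes an AE stop.
- For all-reason discontinuation there is no competing stop reason, so that curve is unaffected.

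**Size.** With constant rates a (AE) and b (other reasons) and time t:

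- one minus Kaplan-Meier = 1 − exp(−a t)
- cumulative incidence = a/(a+b) × [1 − exp(−(a+b) t)]

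For a = 0.02, b = 0.05, t = 4: 1 − exp(−0.08) = 7.69%, against (0.02/0.07) × [1 − exp(−0.28)] = 6.98%. The excess is 0.71 points, or 0.0071 × 120 = 0.85 of a patient.

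| AE rate/yr | Other rate/yr | Years | 1 − KM | Cumulative incidence | Excess (points) | Ratio |
|---|---|---|---|---|---|---|
| 2% | 0% | 4 | 7.69% | 7.69% | 0.00 | 1.00 |
| 1% | 2% | 4 | 3.92% | 3.77% | 0.15 | 1.04 |
| 2% | 5% | 2 | 3.92% | 3.73% | 0.19 | 1.05 |
| 2% | 5% | 4 | 7.69% | 6.98% | 0.71 | 1.10 |
| 2% | 10% | 4 | 7.69% | 6.35% | 1.33 | 1.21 |
| 5% | 10% | 4 | 18.13% | 15.04% | 3.09 | 1.21 |
| 5% | 20% | 4 | 18.13% | 12.64% | 5.48 | 1.43 |

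Over AE rates of 1% to 5% per year, other rates of 0% to 20% per year and 1 to 4 years, the excess runs from 0 to 5.5 points and the ratio from 1.00 to 1.45. With other stops at or below 5% per year the ratio is at most about 1.10.

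**Check at the planned size.** A simulation of 4,000 trials of 120 patients used a = 0.02, b = 0.05 and administrative censoring uniform between 0.5 and 4 years. At 3 years the mean of one minus Kaplan-Meier was 5.84% and of Aalen-Johansen 5.43%, against a true value of 5.41%. The crude proportion over all follow-up was 4.10%.

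**Small groups.** SAP 5.5 repeats the disposition summary for adolescents. As an illustration, suppose 4 of 14 stop for other reasons before a single AE stop, with no other censoring. Kaplan-Meier then shows 1/10 = 10.0%, while 1/14 = 7.1% actually stopped for an AE.

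**The case against.** The strongest reply is that little depends on this curve. It is a descriptive figure under Patient Disposition, there is no formal testing (Protocol 10.1), and counts, percentages, reasons and listings are reported separately. The all-reason curve beside it lets a reader see how much other stopping there was. All of that stands.

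The excess may also be very small. At 2% and 5% per year it is 0.71 points at 4 years. Even with all 120 patients followed that long, the binomial standard error at 7.7% is √(0.077 × 0.923/120) = 2.4 points, so the excess is about 0.3 of a standard error. The parent study had no AE discontinuations in its 24-week double-blind period (Protocol 1). Many patients may end treatment because of regional approval (Protocol 5.1), which is legitimate censoring and does not create this bias. These points limit the size but leave the direction unchanged.

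The censoring of other-reason stops is inferred, because SAP 5.5 is silent. That is correct, and the silence is part of the gap. Labelling the curve as cause-specific one minus Kaplan-Meier would remove the mislabelling, but the plan would still have no estimate of AE-discontinuation incidence over time.

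Three stronger readings are tempting and should not be drawn:

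- **That a primary tolerability outcome, or the main summary of tolerability, is biased.** AE discontinuation is not a named primary endpoint, and no section ranks it as the main summary. It bears on the tolerability objective only.
- **That disagreement between the curve and the crude percentage shows the bias.** In the simulation the gap is 5.84 − 4.10 = 1.74 points, of which Aalen-Johansen removes 5.84 − 5.43 = 0.41. The other 1.33 points, about three quarters, remain under the correct estimator and come mainly from unequal follow-up.
- **That the Continue and New evinacumab groups are distorted relative to each other.** This needs different other-reason dropout in the two groups, on which the documents say nothing, and no comparison of these curves is specified.

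**Conclusion.** The point holds as a minor one. The method named in SAP 5.5 does not estimate the incidence it is said to show once some patients stop for reasons other than an AE and are censored. The direction is certain under that censoring; the size cannot be derived from the documents. It is zero with no other-reason stops, about 0.2 points at 2 years and 0.7 points at 4 years under the central assumed rates, and reaches several points only with other-reason dropout of 10% to 20% per year combined with a 5% AE rate over 4 years. No test, decision rule or sample size is affected.

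**What to change.** In SAP 5.5, keep Kaplan-Meier for all-reason discontinuation. For discontinuation due to AEs, plot an Aalen-Johansen cumulative incidence function with discontinuation for any other reason as the competing event. State the rule in the text: censor only patients still on treatment at the data cut-off or whose treatment ended administratively, for example through regional approval or study closure.

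The cost is an added SAP sentence and a slightly lower curve. No new data are needed, because SAP 4.5 already takes completion and reasons for discontinuation from the e-CRF, and SAP 1 allows revision before database lock.

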5.6. Extent of Study Treatment Exposure and Compliance

The extent of study treatment exposure and compliance for the study described in Section 4.6 will be assessed and summarized by patient group for the study, for patients in the safety analysis set, and again for the subpopulation of adolescent patients.

5.6.1. Exposure to Investigational Product

Study treatment exposure in the study will be descriptively summarized for treatment duration and total number of infusions as described in Section 4.6. Treatment duration (including patient-years) and total number of infusions will be summarized using the number of patients with data, mean, SD, Q1, Q3, median, minimum and maximum. Categorized 4-week intervals of treatment duration will be summarized descriptively by counts and percentages.

5.6.2. Study Treatment Compliance

Descriptive statistics of the infusion frequency will be summarized. Further, study treatment infusion interruptions and incomplete infusions with reason will be summarized by patient count (percentage) and a patient listing will be provided for those patients with incomplete infusions. Cases of study treatment symptomatic overdose will be reported in the AE e-CRF page and will be described in the adverse event analysis.

Both monitored and derived protocol deviations will be summarized for important deviations (counts of deviations), patients (incurring a deviation by count and percentage), and by type of important deviation (patient count and percentage). A patient listing of all important and minor protocol deviations will be provided.

5.7. Analyses of Efficacy Variables

For statistics where international and conventional units do not impact the results (e.g. percent changes from baseline, rates of patients below a threshold), derivations will be calculated and summaries will be run using conventional units. For other statistics (e.g. values at baseline and over time, absolute changes from baseline), derivations will be presented in both international and conventional units.

Descriptive analyses for the efficacy endpoints will be conducted as described below.

5.7.1. Analyses of Efficacy Variables

The observed percent and absolute change in lipid parameters (e.g., LDL-C, Apo B, TG, etc.) will be descriptively summarized for each visit, and by patient group for the study for patients in the SAF, and again for the subpopulation of adolescent patients for patients in the SAF. A within-patient t-test (lipids with a normal distribution) or Wilcoxon signed-rank test (non-parametric test for lipids with a non-normal distribution such as TG) will be provided for secondary efficacy endpoints to descriptively compare each patient's week 24 assessment to their baseline assessment. Missing data will not be imputed.

Unless otherwise specified, the baseline value used for determining percent and absolute change for each patient is defined as follows (also see in Section 6.1).

- For patients who participated in previous evinacumab study R1500-CL-1629, baseline is defined as the last obtained value before the first dose of double-blind study drug in R1500-CL-1629.
- For patients who participated in previous evinacumab study R1500-CL-1331 or did not participate in any previous evinacumab study, baseline is defined as the last obtained value before the first dose of study drug in R1500-CL-1719 (Note: Baseline for patients who participated in R1500-CL-1331 is defined as the baseline from the R1500-CL-1719 study due to the long time between the last study treatment in R1500-CL-1331 and the first study treatment in R1500-CL-1719).

For patients who participated in previous evinacumab study R1500-CL-1629 and received evinacumab in the DBTP, a combined summary of LDL-C including both the DBTP and OLTP assessments in R1500-CL-1629 study and the assessments in R1500-CL-1719 study (i.e., with DBTP first dose date in R1500-CL-1629 study as starting point) will be considered, referencing the double-blind baseline for variable calculations.

For patients who participated in previous evinacumab study R1500-CL-1629 and received placebo in the DBTP but received evinacumab in the OLTP, a combined summary of LDL-C including OLTP assessments in R1500-CL-1629 study and the assessments in R1500-CL-1719 study (i.e., with OLTP first dose date in R1500-CL-1629 study as starting point) will also be considered, referencing the double-blind baseline for variable calculations.

A combined summary of LDL-C assessments when receiving study R1500-CL-1629 evinacumab in the DBTP and OLTP for the above two groups of patients will also be considered.

Prolonged time between last dose of DBTP treatment and first dose of OLTP treatment in R1500-CL-1629 study, or between last dose of OL TP treatment in R1500-CL-1629 study and first dose of open-label treatment in R1500-CL-1719 study will need to be taken into consideration when combining longitudinal efficacy data. Formal statistical testing is not planned.

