10.1. Statistical Hypothesis

No formal statistical testing will be performed for this open-label study.

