10.4.3. Efficacy Analyses

The percent and absolute change in lipid data (eg, LDL-C, Apo B, TG) will be descriptively summarized for each visit by the status of previous evinacumab treatment exposure for all patients in the SAF, and again for the subpopulation of adolescent patients [yes/no] for patients in the SAF. A within-patient t-test (lipids with a normal distribution) or Wilcoxon signed-rank test (non-parametric test for lipids with a non-normal distribution such as TG) will be provided for secondary efficacy endpoints to descriptively compare each patient's week 24 assessment to their baseline assessment. Missing data will not be imputed.

The baseline value used for determining percent and absolute change for each patient is defined as follows:

- For patients who participated in the previous evinacumab study R1500-CL-1629, baseline is defined as the last obtained value before the first dose of double-blind study drug in R1500-CL-1629.
- For patients who participated in the previous evinacumab study R1500-CL-1331 or did not participate in any previous evinacumab study, baseline is defined as the last obtained value before the first dose of study drug in R1500-CL-1719. (Note: Baseline for patients who participated in R1500-CL-1331 is defined as the baseline from the R1500-CL-1719 study due to the long time between the last study treatment in R1500-CL-1331 and the first study treatment in R1500-CL-1719.)

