2.2. Sample Size and Power Considerations

Since this study is an open-label single treatment arm study for patients with HoFH, no calculation for sample size was performed. Approximately 120 patients will be enrolled.

[figure not shown]
To gain experience with evinacumab in the subpopulation of adolescent patients, this study will plan to enroll approximately 14 patients in the age range of 12 years to < 18 years old. Due to the rare patient population planned for evaluation, the sample size of 14 patients was chosen for practical reasons, centered on the feasibility to identify and enroll these patients into the trial and regulatory precedent.

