5. STATISTICAL METHODS

In general, data will be summarized and presented in three patient groups, depending on the status of previous evinacumab treatment exposure:

- Continue Evinacumab: Patients who received evinacumab in a previous study (eg, R1500-CL-1331 or R1500-CL-1629);
- New Evinacumab: Patients without previous exposure to evinacumab (ie, evinacumab naïve);
- Total: All patients, regardless of previous (or not) evinacumab exposure.

These 3 evinacumab exposure groups will be provided for all patients in the respective patient analysis sets. Assuming there are enough adolescent patients (age ranging from 12 years to < 18 years old) to perform an evaluation, the three evinacumab treatment exposure groups will be provided again for the subpopulation of adolescent patients [yes/no]. The subpopulation of adolescent patients has two categories, specifically the patient is an adolescent defined as ranging in age from 12 years to < 18 years old, or the patient is not an adolescent (i.e. an adult) defined as ≥ 18 years of age. Unless otherwise noted, data from both adolescent and adult patient subgroups will be summarized.

Continuous data will be summarized descriptively using the number of patients with data, mean, SD, median, minimum and maximum for each patient group for the study. First quartile (Q1) and third quartile (Q3) will be also provided for baseline lipid parameters, HbA1c, and hs-CRP.

Categorical and ordinal data will be summarized using the number and percentage of patients for each patient group for the study.

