5.8. Analysis of Safety Data

Safety summaries for the study will be presented by patient group for the study in the safety analysis set, and again for the subpopulation of adolescent patients. No formal inferential testing will be performed. Summaries will be descriptive in nature.

All safety analyses will be performed using the baseline definitions described in Section 6.1.

General common rules

All safety analyses will be performed, unless otherwise specified, using the following common rules:

- Safety data in patients who do not belong to the safety analysis set (e.g., exposed but not enrolled) will be listed separately.
- The potentially clinically significant value (PCSV) values are defined as abnormal values considered medically important by the Sponsor according to predefined criteria/thresholds based on literature review and defined by the Sponsor for clinical laboratory tests and vital signs (PCSV version dated January 2009 [Appendix 10.4]).

Considering that the threshold defined in the PCSV list for monocytes and basophils can be below the ULN, the following PCSV criterion will be used for the PCSV analysis of monocytes and basophils:

- PCSV criterion for monocytes: >0.7 Giga/L or >ULN (if ULN ≥0.7 Giga/L).
- PCSV criterion for basophils: >0.1 Giga/L or >ULN (if ULN ≥0.1 Giga/L).

- PCSV criteria will determine which patients had at least 1 PCSV during the TEAE period, taking into account all evaluations including unscheduled or repeated evaluations.
- The treatment-emergent PCSV denominator by patient group for a given parameter will be based on the number of patients assessed for that given parameter at least once during the TEAE period.
- All measurements, scheduled or unscheduled, fasting or not fasting, will be assigned to Global Analysis Windows defined in Appendix 10.2 /Table 1 in order to provide an assessment for the screening visit through follow-up visit time points.
- For quantitative safety parameters including central laboratory measurements and vital sign scores, descriptive statistics will be used to summarize observed values and change from baseline values by visit.
- Open-label treatment period (OLTP): The treatment period used for quantitative analysis of laboratory and vital signs data in the open-label study period is defined from the day after the first dose of open-label study treatment to the day of the last dose of open-label study treatment + 28 days.

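### The week-24 lipid comparison is a test against no change, and no confidence interval is planned for any lipid change, adverse-event proportion or event rate, including in the roughly 14 adolescents

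*SAP*

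**What the plan says.** Protocol 10.1 states: "No formal statistical testing will be performed for this open-label study". SAP 5.7.1 closes with "Formal statistical testing is not planned", and SAP 5.8 says of safety: "No formal inferential testing will be performed".

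Both documents nevertheless include one inferential procedure. SAP 5.7.1 gives it as "A within-patient t-test (lipids with a normal distribution) or Wilcoxon signed-rank test (non-parametric test for lipids with a non-normal distribution such as TG"), applied to the secondary efficacy endpoints "to descriptively compare each patient's week 24 assessment to their baseline assessment". Protocol 10.4.3 has the same provision, which "will be provided for secondary efficacy endpoints to descriptively compare each patient's week 24 assessment to their baseline assessment". No alpha, decision rule or use of the result is stated.

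The remaining outputs are summaries. SAP 5 says: "Continuous data will be summarized descriptively using the number of patients with data, mean, SD, median, minimum and maximum for each patient group". Quartiles are added for some variables. Categorical data get counts and percentages. SAP 5.8.1 adds an event rate per patient-year, censored at the first event, as a point estimate. Standard errors are mentioned only for plots of laboratory, vital-sign and certain other variables (SAP 5.8.3, 5.8.4 and 5.9). Confidence interval appears in the SAP abbreviation list but in no analysis section.

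Long-term safety in adolescents is a primary objective and their lipid response a secondary one (SAP 1.2.1 and 1.2.2). About 14 are planned, and "the sample size of 14 patients was chosen for practical reasons". SAP 7 calls their 24-week analysis the final one for both sets of endpoints. No statement of precision goes with it.

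**The concern.** Without a control arm, a within-patient test asks only whether the mean or median change differs from zero. For LDL-C that is hardly in doubt, given the parent-study result in Protocol Section 1. What a reader wants to know is how large the change is and how well it is estimated, and a p-value answers neither.

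The primary endpoint is safety, and there the plan gives only counts and percentages. In a group of 14, a line reading 0 of 14 for an adverse event of special interest can be taken as reassurance that the data cannot give. The adolescent result will be reported on its own as final, so the tables should show how precise it is.

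**Working it through.** **The plan's own figure.** There is nothing to reproduce. Protocol 10.2 and SAP 2.2 say that no sample-size calculation was done and give no SD, effect size or precision target.

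**Inputs.** Adolescents: n = 14 (SAP 2.2). All patients: n = 120 (same section). LDL-C change on evinacumab in R1500-CL-1629: −47% at week 24 (Protocol Section 1). Adverse-event rates in the evinacumab arm of that study: 7% rhinorrhea and 11% influenza-like illness (same section). The SD of percent change in LDL-C is not given. I assume 20 to 30 points, and also show 15 to 40.

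**Adverse-event proportions (Clopper-Pearson, two-sided 95%).**
- 0 of 14: upper limit = 1 − 0.025^(1/14) = 23.2%.
- 1 of 14: 0.2% to 33.9%.
- 2 of 14: 1.8% to 42.8%.
- For comparison, 0 of 120: upper limit 3.0%.

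The chance of seeing at least one case in 14 is 1 − (1 − p)^14. It is 51% at a true rate of 5%, 64% at 7% and 80% at 11%. An event as common as rhinorrhea in the parent study would be missed entirely about one time in three.

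**LDL-C percent change.** Half-width = t(0.975, 13) × SD / √14 = 2.160 × SD / 3.742 = 0.577 SD.

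| Assumed SD | Half-width, n = 14 | Interval around −47 | t-test p | Half-width, n = 120 |
|---|---|---|---|---|
| 15 | 8.7 | −55.7 to −38.3 | 3 × 10⁻⁸ | 2.7 |
| 20 | 11.5 | −58.5 to −35.5 | 8 × 10⁻⁷ | 3.6 |
| 30 | 17.3 | −64.3 to −29.7 | 6 × 10⁻⁵ | 5.4 |
| 40 | 23.1 | −70.1 to −23.9 | 0.0007 | 7.2 |

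The p-value is below 0.001 in every row, while the half-width varies from about 9 to 23 points. The interval would reach zero only at an SD of about 47 / 0.577 = 81 points.

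**If the 14 are split by previous exposure.** SAP 5 allows this if numbers suffice; the split is unknown. A cell of 7 has a half-width of 0.92 SD, and a cell of 5 has 1.24 SD. With 5 patients the smallest two-sided exact Wilcoxon p is 2/2⁵ = 0.0625, so that test could not fall below 0.05 even if every patient improved.

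**The case against.** The strongest reply is that the plan disclaims only formal testing and presents the week-24 comparison as descriptive. No hypothesis, alpha or success criterion depends on it. That stands. A reader might infer that the documents contradict themselves, but the wording does not support this: a descriptive test can sit beside a statement that no formal testing is done. The closing sentence of SAP 5.7.1 also ends a paragraph on combining data across two studies and may apply only there.

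A reader might also multiply endpoints by exposure groups and age groups and infer a multiplicity problem. The documents do not support that either. The group breakdown is in the sentence on descriptive summaries, the sentence on the test does not repeat it, and the adolescent split is conditional on numbers. With no decision rule, a count of tests has no consequence.

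It can be said, too, that little information is lost. Intervals for means can be worked out from n, mean and SD, and exact intervals from counts. That is largely true, though not for the triglyceride median. It is a reason why the change is cheap rather than a reason to leave the intervals out of a final analysis.

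Finally, follow-up runs from months to about 4 years (SAP 2.3), so an exact interval on a whole-study proportion mixes unequal exposure. This is a fair criticism, and the remedy has to deal with it.

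**Conclusion.** The point holds as a reporting improvement. The only inferential output is a test that carries little information on effect size, and the primary adolescent safety results have no measure of precision. The size for safety is firm because it needs only n = 14: up to 23.2% after no events, and 0.2% to 33.9% after one.

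A reader might infer that 14 adolescents can establish little about lipids. That does not follow. With a mean near −47%, the LDL-C interval excludes zero for any SD below about 81 points. What it would show is that the size is known to about ±0.58 SD, or 11.5 to 17.3 points for SDs of 20 to 30. This rests on the assumed SD and on adolescents responding like the parent-study arm. The numerical argument is for LDL-C: Protocol Section 1 reports significant reductions in Apo B, non-HDL-C and total cholesterol without their size, and gives no triglyceride result.

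**What to change.** **SAP 5.7.1.** Report mean percent and absolute lipid change with 95% confidence intervals as the main output. For triglycerides, report the median with a distribution-free 95% interval. Keep the t-test and Wilcoxon test if wanted, and label their p-values nominal. This keeps the SAP in line with Protocol 10.4.3. Removing the tests would depart from the protocol and would need an entry in SAP 1.2.3, which now lists no modifications.

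**SAP 5.8.1 and 5.8.2.** Add exact (Clopper-Pearson) 95% intervals for any TEAE, any serious TEAE, each adverse event of special interest and discontinuation due to an adverse event. Do this in the adolescent 24-week analysis and in the Total group. Add 95% intervals for the event rates per patient-year already planned, and read long-term safety from those rates because follow-up is unequal.

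**Cost.** SAP wording and modest programming, with no new data or visits. SAP Section 1 allows revision before database lock.
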